1.2 Study objectives and endpoints

[figure not shown]
Table 1-1 Objectives and related endpoints

[figure not shown]
Objective(s)	Endpoint(s)
Primary objective(s)	Endpoint(s) for primary objective(s)

 To evaluate the efficacy of retreatment with ligelizumab 72 mg or 120 mg q4w in subjects previously treated in the core studies (CQGE031C2302/CQGE031C2303) To evaluate the efficacy of retreatment with ligelizumab in the subgroup of these subjects who achieved a weekly urticaria activity score (UAS7) ≤ 6 after 12 weeks of treatment in these core studies 	
 The proportion of subjects with well-controlled disease (UAS7 ≤ 6) at Week 12
Secondary objective(s)	Endpoint(s) for secondary objective(s)
For retreatment efficacy evaluation:	

 To describe the efficacy of ligelizumab 72 mg or 120 mg q4w in achieving complete control of chronic spontaneous urticaria (CSU) at Week 12 when used as retreatment for subjects previously treated in the core studies (CQGE031C2302/CQGE031C2303) To describe the efficacy of ligelizumab with respect to a reduction from extension study baseline in the UAS7 and its components (weekly itch severity score (ISS7) and weekly hives severity score (HSS7) at Week 12 in all subjects receiving the same dose regimen as in the core studies, i.e. 72 mg or 120 mg q4w To describe the efficacy of ligelizumab in achieving an angioedema-free period at Week 12 in all subjects receiving the same dose regimen as in the core studies, i.e. 72 mg or 120 mg q4w 	
 The proportion of subjects with completely controlled disease (UAS7 = 0) at Week 12 Absolute change from extension study baseline in the UAS7 and its components (ISS7 and HSS7) at Week 12 Cumulative number of weeks that subjects achieve weekly angioedema activity score (AAS7) = 0 between extension study baseline and Week 12

Objective(s)	Endpoint(s)

To describe the efficacy of ligelizumab in achieving Dermatology Life Quality Index (DLQI) = 0-1 at Week 12 when used as re-treatment for all subjects receiving the same dose regimen as in the core studies, i.e. 72 mg or 120 mg q4w	
Percentage of subjects achieving DLQI = 0-1 at Week 12
For self-administration efficacy evaluation:	

To describe the efficacy of ligelizumab in the treatment of CSU, 12 weeks after starting self-administration	
The proportion of subjects with well-controlled disease ($UAS7 \leq 6$), 12 weeks after starting self-administration
For safety & tolerability evaluation:	

To assess the safety and tolerability of ligelizumab in all subjects	
In each dose group, and for each duration of treatment:
 
Occurrence of treatment emergent adverse events during the studyOccurrence of treatment emergent serious adverse events during the studyVital signsLab assessments

To assess the safety and tolerability of ligelizumab 120 mg q4w 1mL pre-filled syringe (PFS)	
For the duration of treatment:
 
Occurrence of treatment emergent serious adverse events during study Week 12 onwardsVital signs Week 12 onwardsLab assessments Week 12 onwards

To assess the safety and tolerability of ligelizumab 120 mg q4w in all subjects who self-administer	
Occurrence of treatment emergent adverse eventsOccurrence of treatment emergent serious adverse eventsVital signsLab assessments

Objective(s)

Endpoint(s)

On 06 April 2022, following extensive assessment of data from the Phase III studies (CQGE031C2302, CQGE031C2303) of ligelizumab in CSU, Novartis communicated a strategic decision to discontinue further clinical development of ligelizumab in chronic urticaria (CSU and chronic inducible urticaria (CINDU)). The decision to not proceed was not based on

any safety concerns with ligelizumab. As a result of this decision, this study CQGE031C2302E1 was terminated.

2 Statistical methods

2.1 Data analysis general information

Data will be analyzed by the Novartis team internally following the protocol section 12, using SAS version 9.4 or above.

DMC analyses will be done by the independent statistician and programmers in a separate CRO. Statistical Analysis Plan for the DMC analyses will be prepared separately.

The first interim analysis is planned once all subjects from the CQGE031C2302 and CQGE031C2303 have completed Week 12 (Visit 204) in the first half of the treatment period to evaluate the primary endpoint of retreatment efficacy.

The second interim analysis will be performed at the end of the first half of the treatment period once all treated subjects completed the first half of the treatment period (see below for rules of cutoff) to evaluate endpoints up to the end of 1 year treatment:

- Subjects who enter the second half of the treatment period without going to the second observation period: data up to and including visit 214 (excluding the DAR page)
- Subjects who enter the second observation period: data up to and include visit 301
- Subjects who discontinue prior to visit 214: all data up to date of study discontinuation

Additional interim analyses may be performed to support health authority interactions as necessary.

All analyses (including safety, [REDACTED] and efficacy, except for some lab parameters and the DLQI/CDLQI questionnaire), will be provided for adolescents and the adults combined, unless stated otherwise. [REDACTED]

Adolescents (<18 years old) or adults (\geq 18 years old) will be determined based on the baseline age at the time of enrollment, unless it is specified otherwise.

The general descriptive statistical rules for summarizing the categorical data and continuous data are provided below:

All categorical data will be summarized by frequencies and percentages. The frequencies and percentages will also be presented for missing observations.

Continuous data will be summarized with either standard descriptive statistics (i.e. the number of non-missing data points, arithmetic mean, standard deviation, minimum, 25% percentiles(Q1), median, 75% percentiles (Q3) and maximum), or will be collapsed into categorical data and be summarized as categorical data.

2.1.1 General definitions

2.1.1.1 Study Treatment

Study treatment groups used for analysis are defined as below:

- ligelizumab 72 mg q4w liquid in vial – ligelizumab 120 mg q4w PFS
- ligelizumab 120 mg q4w liquid in vial – ligelizumab 120 mg q4w PFS

2.1.1.2 Study periods

The following study periods will be considered for analysis:

- Screening period (SCR): from the date of signing informed consent form (ICF) to, and not include the date of the first ligelizumab treatment (i.e. V201) in extension, or the first visit in the first observation period (i.e. V101), whichever comes first.
- First observation period (OBS1): from Visit 101 up to Visit 199. The duration of OBS1 period for each subject varies, as it depends on occurrence of relapse ($UAS7 \geq 16$). Maximum duration of OBS1 is 36 weeks.
- First 12 weeks of the first half of the treatment period (TRT1A): from Visit 201 to Visit 204.
- Week 12 to Week 52 of the first half of the treatment period (TRT1B): from Visit 204 to Visit 214 or 301, whichever comes first.
- Entire first half treatment period (TRT1): from Visit 201 to Visit 214 or 301, whichever comes first.
- Second observation period (OBS2): from Visit 301 up to Visit 399. The duration of OBS2 period for each subject varies, as it depends on occurrence of relapse ($UAS7 \geq 16$). Maximum duration of OBS2 is 52 weeks.
- Second half of the treatment period (TRT2): Visit 214 to Visit 9998 (excluding Visit 301 to Visit 399)
- Follow-up period:
 - Subjects who do not complete a continuous 104-week treatment will enter the follow-up period (FU12) for 12 weeks duration and will only perform Visit 9999.
 - Subjects who have completed the full 104-week treatment period without interruption will enter the follow-up period (FU52) of 52 weeks duration and will perform Visit 501 to Visit 9999 (Week 116 to Week 156).

2.1.1.3 Study Day and Study Week

2.1.1.3.1 Study Day

Study day is defined with respect to extension and will be used for all efficacy and safety analyses. The first day of administration of study treatment (first dose) of extension study is defined as Day 1.

All other study days will be labeled relative to Day 1. For event dates on or after Day 1, study day for a particular event date will be calculated as [Date of event] - [Date of first dose] + 1. For the dates before Day 1, study day for an event date will be calculated as [Date of event] - [Date of first dose]. Hence, study days for the following critical dates are defined as follows:

- Signing ICF (Day *a*) : [Date of signing ICF] - [Date of first dose]
- Start of OBS1 (Day *b*): [Date of Visit 101] - [Date of first dose]
- Start of TRT1 (Day 1): defined as Day 1
- Start of TRT2 (Day *c*): [Date of Visit 214] - [Date of first dose] +1
- Start of OBS2 (Day *d*): [Date of Visit 301] - [Date of first dose] +1
- Start of 52-week FU (Day *e*): [Date of Visit 501] - [Date of first dose] +1

Duration of an event will be calculated as (Event end date - Event start date + 1).

The descriptor “Day 0” will not be used.

2.1.1.3.2 Study week in the treatment period

The *study week in the treatment period* defined in this section will be used for the primary and secondary efficacy analyses based on the eDiary. Other assessments collected on Rave CRF visit will be analyzed according to the CRF collected visit weeks. Note that the “baseline week” (Baseline) is comprised of the 7 days prior to Day 1 (Day -7 to Day -1).

For all subject in SAF, study weeks (Week *x*) in the first half of the treatment period (including 12 week-follow up in case of early discontinuation) are defined based on the study days as indicated in Table 2-1:

Table 2-1 Study Week definition based on Study Day, first half of the treatment period (including 12 week-follow up in case of early discontinuation)

Study Week (x)	Study Days
Baseline	Day (-7) ~ (-1)
Week 1	Day 1 ~ 7
...	...
Week x	Day $[7 \times (x-1) + 1] \sim [7 \times x]$
...	...

Study Week (x)	Study Days
Week 52	Day 358 ~ 364

For subjects who **enter the second half of the treatment period without entering OBS2** (including subjects in the continuous long term treatment subpopulation), study weeks (Week x) in the second half of the treatment period (including 12 week-follow up in case of early discontinuation) are defined based on the study days as indicated in Table 2-2a:

Table 2-2a Study Week definition based on Study Day, second half of the treatment period (including 12 week-follow up in case of early discontinuation), for subjects who enter the second half of the treatment period without entering OBS2

Study Week (x)	Study Days
Week 52	Day 358 ~ 364
...	...
Week x	Day $[7 \times (x-52) + 358] \sim [7 \times (x-51) + 357]$
...	...
Week 104	Day 722 ~ 728

For subjects who **enter the second half of the treatment period after entering OBS2** (i.e. subjects in the long-term treatment with a rest subpopulation), study weeks (Week x) in the second half of the treatment period (including 12 week-follow up in case of early discontinuation) are defined based on the study days and study day of Visit 214 (Day c) as indicated in Table 2-2b:

Table 2-2b Study Week definition based on Study Day, second half of the treatment period (including 12 week-follow up in case of early discontinuation) , for subjects who enter the second half of the treatment period after entering OBS2

Study Week (x)	Study Days
Week 52 (V214)	Day $c \sim 6+c$
...	...
Week x	Day $[7 \times (x-52) + c] \sim [7 \times (x-51) + c - 1]$
...	...
Week 104	Day $364+c \sim 370+c$

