3.3 First half of the treatment period

- Week 0 (Visit 201) to Week 52
- Subjects receive their first dose of ligelizumab at Visit 201 (Week 0) and last dose of ligelizumab of this first half of the treatment period at Visit 213 (Week 48).
- Subjects must remain on the same H1-AH background medication they were taking in the preceding studies.
- Subjects should use the same H1-AH rescue medication that was agreed with the investigator at Visit 1 of this study.
- Oral corticosteroid rescue medication is permitted only at and after Visit 204 (Week 12) (after all assessments are completed), with the limitations as per protocol (see [Section 6.2.3](#)).
- Subjects entering the first half of the treatment period from the preceding studies will be assigned to treatment as follows:
 - Core studies CQGE031C2302 and CQGE031C2303:
 - For the first 12 weeks, the blinded treatment assignment will be determined according to the treatment group assignment during the core studies following these rules:
 - Subjects treated with ligelizumab 72 mg liquid in vial s.c. q4w in the core studies will be treated with ligelizumab 72 mg liquid in vial s.c. q4w in a double-blind manner such that their prior treatment regimen will not be unblinded.
 - All other subjects from the core studies will be treated with ligelizumab 120 mg liquid in vial s.c. q4w in a double-blind manner such that their prior treatment regimen will not be unblinded.

- Studies CQGE031C1301 and CQGE031C2202:
 - All subjects from these studies will be treated with ligelizumab 120 mg liquid in vial s.c. q4w in an open-label manner for the first 12 weeks.
- If the subject in the screening period or first observation period presents with moderate to severe disease, defined as $UAS7 \geq 16$, the subject will enter the treatment period at Visit 201 (Week 0), and start the treatment assigned as above.
- At Visit 204 (Week 12), all subjects will be switched to ligelizumab 120 mg s.c. pre-filled syringe (PFS) q4w in an open-label manner.
- At Visit 204 (Week 12) subjects will be offered an opportunity to administer ligelizumab outside the clinic. For details regarding self-administration outside of the clinic and monitoring post ligelizumab administration, see [Section 6.7.2](#).
- All subjects, whether in the clinic-administered or outside the clinic self-administered group will continue to complete the eDiary twice daily as per protocol.

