The first visit of the extension study, if it cannot occur on same day as the last visit (Visit 1999) of the preceding studies, as described in [Section 3.1](#) and [Section 8.1](#), should occur within as short time as possible from the last visit of the preceding studies. In this case, the Investigator must perform a thorough review of new medical histories and concomitant medication changes from the time of the last visit of the preceding studies until the first visit of this extension study.

Assessment schedule ([Table 8-1](#) and [Table 8-2](#)) lists all of the assessments and when they are performed. All data obtained from these assessments must be supported in the subject's source documentation.

Subjects should be seen for all visits/assessments as outlined in the assessment schedule ([Table 8-1](#) and [Table 8-2](#)) or as close to the designated day/time as possible. Missed or rescheduled visits should not lead to automatic discontinuation. Subjects who prematurely discontinue the study or withdraw their consent/oppose the use of their data/biological samples for any reason should be scheduled for a visit as soon as possible, at which time all of the assessments listed for the final visit (Visit 9999/EOS) will be performed. At this final visit, all dispensed investigational product should be reconciled, and the AE and concomitant medications recorded on the CRF.

As per [Section 4.6](#), during a Public Health emergency as declared by Local or Regional authorities, i.e., pandemic, epidemic or natural disaster that limits or prevents on-site study visits, alternative methods of providing continuing care may be implemented by the investigator as the situation dictates. If allowable by a local Health Authority and depending on operational capabilities, phone calls or virtual contacts (e.g., tele consult), can replace on-site study visits, for the duration of the disruption until it is safe for the participant to visit the site again.

[figure not shown]
Table 8-1 Assessment Schedule (Screening, First and Second half of the treatment period and Follow-up period)

Epoch	Screening		-----First half of the Treatment----->																								-----Second half of the Treatment----->			
	Visit Numbers ¹	1 ²	2 ³	201	202	203	204	205	206	207	208	209	210	211	212	213	214 ^{4,5}	401	402	403	404	405	406	407	408	409	410	411	412	9998

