12.4 Analysis of the primary endpoint(s)

12.4.1 Definition of primary endpoint(s)

The primary endpoint is the proportion of subjects with well-controlled urticaria at Week 12 (Visit 204) in the first half of the treatment period based on the UAS7 score. Well-controlled urticaria at Week 12 is assessed as achieving $UAS7 \leq 6$ at Week 12.

The UAS7 is the sum of the HSS7 score and the ISS7 score, and ranges from 0-42. Weekly scores (HSS7 and ISS7 scores) will be derived by adding up the average daily scores of the 7 days preceding the visit.

Regardless of the use of rescue medication or discontinuation of the study assigned-treatment due to any reason up to the assessment time point, all available data collected for UAS7 scores will be used for primary endpoint calculation.

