2.5.3 Handling of missing values/censoring/discontinuations

The UAS7 score is derived from the sum of the HSS7 score and the ISS7 score, as noted above. The HSS7 and ISS7 score will be derived by adding up the daily HSS and ISS scores of the 7 days preceding the visit, respectively. The daily score (HSS and ISS) will be calculated by averaging the morning and evening HSS and ISS score, respectively. If one of the morning or evening scores is missing, the non-missing score for that day (morning or evening) will then be used as the daily score.

A minimum of 4 out of 7 daily scores are needed to reliably calculate a weekly HSS7, ISS7 or UAS7 score. For each weekly score from UPDD (i.e. HSS7, ISS7 and UAS7 score), if one or more of the daily scores are missing, the following principles will be applied to handle the missing data:

- If a subject has at least 4 “non-missing” daily scores within the 7 days prior to the study visit, the weekly score will be calculated as the sum of the available eDiary scores of that week, divided by the number of non-missing days, multiplied by 7.
- If there are less than 4 “non-missing” daily scores within the prior 7 days, then the weekly score will be considered as missing for that week.

Subjects who discontinue from study treatment early will be encouraged to stay in the study following the procedures described in the study protocol Section 9.1.1. These are considered as retrieved dropout (RDO) subjects.

The primary analysis will account for different post-dosing events for missing data handling as follows:

- Discontinuation of initially assigned study treatment prior to Week 12 (Visit 204) due to AEs or lack of efficacy or any other reasons, except for the reason of study early termination: Retrieved dropout (RDO) data collected after study treatment discontinuation will be used for analysis. If no RDO data was collected after study treatment permanent discontinuation, non-responder imputation will be applied for missing data imputation.
- Discontinuation of initially assigned study treatment prior to Week 12 (Visit 204) due to study early termination: the efficacy data collected after the discontinued treatment will be censored. The missing data caused by this intercurrent event occurrence will be imputed based on the treatment arm (ligelizumab 72 mg or 120 mg q4w) data under the missing at random (MAR) assumption using multiple imputation separately.

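### The Week 12 primary score has two windows that agree only when Visit 204 falls on Day 85, and the fixed window takes in days after the switch to open-label 120 mg when that visit is early

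*SAP*

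**What the plan says.** **Fixed window.** SAP 2.1.1.3.1 sets the origin: "The first day of administration of study treatment (first dose) of extension study is defined as Day 1". SAP 2.1.1.3.2 states that the study week "defined in this section will be used for the primary and secondary efficacy analyses based on the eDiary". Table 2-1 gives Week x by a formula in days from first dose, with no reference to the visit date.

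**Visit-anchored window.** Protocol 12.4.1 has the weekly scores "derived by adding up the average daily scores of the 7 days preceding the visit". SAP 2.5.3 forms HSS7 and ISS7 by "adding up the daily HSS and ISS scores of the 7 days preceding the visit" and applies its four-day minimum to "daily scores within the 7 days prior to the study visit". Protocol 12.4.3 has the same wording. SAP 2.5.1 ties the primary time point to Visit 204.

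**What happens at Visit 204.** Protocol 3.3: "At Visit 204 (Week 12), all subjects will be switched to ligelizumab 120 mg s.c. pre-filled syringe (PFS) q4w in an open-label manner". The same section opens oral corticosteroid rescue at that visit once the assessments are done.

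**Visit timing.** Table 8-1 of the protocol puts Visit 204 on Day 85. Protocol section 8 asks that visits take place as scheduled "or as close to the designated day/time as possible". The text gives no numeric window.

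**Departures from the protocol.** SAP section 4 records none.

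**The concern.** The primary endpoint is meant to measure 12 weeks of blinded retreatment, from the vial, at the dose given in the core studies. The protocol protects this in several ways. It keeps 72 mg until Visit 204 and starts the PFS only then, so that Week 12 can be compared with the preceding studies (4.2). It holds corticosteroid rescue until after the Week 12 assessments (6.2.3). It blinds the dose to avoid bias in the primary assessment (4.1).

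A window fixed in days from first dose does not respect that boundary. For a subject seen early, it continues past the first PFS dose. A 72 mg subject is then scored partly on 120 mg. A 120 mg subject keeps the same dose but is scored partly on an open-label syringe. In both arms corticosteroid rescue may be in use.

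For a late visit there is no contamination, but the two rules score different parts of the dosing interval. Protocol 4.2 reports partial return of symptoms towards the end of the interval at 24 and 72 mg, so the part that is scored could matter.

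Two programmers working from different sections of the same SAP could therefore build different primary datasets.

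**Working it through.** **Inputs**
- Week x = Day 7(x-1)+1 to Day 7x (SAP Table 2-1).
- Day 1 = first extension dose (SAP 2.1.1.3.1).
- Visit 204 is nominally on Day 85 (Protocol Table 8-1).
- The visit-anchored window for a visit on Day v is Day v-7 to Day v-1 (SAP 2.5.3, Protocol 12.4.1).
- Daily HSS and daily ISS each run from 0 to 3 (SAP Tables 5-2 and 5-3), so one day contributes at most 6 to UAS7.

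**Reproducing the SAP's own row.** For x = 52: 7 × 51 + 1 = 358 and 7 × 52 = 364, as Table 2-1 prints. For x = 12: 7 × 11 + 1 = 78 and 7 × 12 = 84. Week 12 is therefore Days 78-84.

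**Comparing the windows.** The largest possible difference is 6 × (7 - shared days), with complete diaries.

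| Visit 204 on Day | Visit-anchored window | Days shared with 78-84 | Fixed-window days on or after the visit day | Of these, wholly after | Largest UAS7 difference |
|---|---|---|---|---|---|
| 78 | 71-77 | 0 | 7 | 6 | 42 |
| 81 | 74-80 | 3 | 4 | 3 | 24 |
| 82 | 75-81 | 4 | 3 | 2 | 18 |
| 83 | 76-82 | 5 | 2 | 1 | 12 |
| 84 | 77-83 | 6 | 1 | 0 | 6 |
| 85 | 78-84 | 7 | 0 | 0 | 0 |
| 86 | 79-85 | 6 | 0 | 0 | 6 |
| 88 | 81-87 | 4 | 0 | 0 | 18 |
| 92 | 85-91 | 0 | 0 | 0 | 42 |

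**The visit day.** With Visit 204 on Day 85-k, the fixed window contains k days from the visit day onward, of which k-1 lie wholly after it. The daily score averages a morning and an evening entry, each covering the past 12 hours. Protocol 8.3 has the eDiary assessment completed before dosing. If the morning entry precedes the dose and the evening entry follows it, the post-switch share is (k - 0.5)/7:
- k = 1: 0.5/7 = 7%
- k = 3: 2.5/7 = 36%
- k = 4: 3.5/7 = 50%

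Counting the whole visit day would give 1/7 = 14%, 3/7 = 43% and 4/7 = 57%.

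**Effect of moving the window on the AAS7 count.** Take Visit 204 on Day 82. A shifted Week 12 is Days 75-81, while Week 11 is Days 71-77, so Days 75-77 would count twice in the cumulative number of weeks with AAS7 = 0. If Week 12 stays at Days 78-84 and Days 82-84 are dropped, Days 78-81 remain. That is 4 days, which just meets the four-day minimum. In general 7-k days remain, so the minimum can be met only for k up to 3.

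**The case against.** **The SAP arguably does choose.** SAP 2.1.1.3.2 names the primary analysis expressly, and the visit wording in SAP 2.5.3 is carried over from Protocol 12.4.3, where it mainly serves the rule for missing diary days. This has some force. But SAP 2.5.3 is the section that derives the primary score and states its window twice, and SAP section 4 records no departure from the protocol. If the fixed window does prevail, the post-switch days come with it.

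**The study periods might cap the window.** SAP Table 2-9 places the retreatment secondary endpoints in TRT1A, which SAP 2.1.1.2 ends at Visit 204. That is not stated for the primary endpoint, which Table 2-16 lists under TRT1 up to Week 52. No sentence cuts the Week 12 window at the first PFS dose.

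**The analysis is descriptive.** SAP 2.5.2 plans no inferential testing, so no type I error is at stake. The estimate and its interval are still the primary result.

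**Stronger readings that the documents do not support**
- A reader might infer that every subject seen off Day 85 gets a different responder call. Different windows do not imply that. A visit one day off shares 6 of 7 days, and the call changes only if the unshared days carry the score across 6.
- A reader might infer that treatment assignment is revealed. Only the current dose is open-label. Protocol 4.1 and 6.4 keep the earlier assignment blinded until the Week 12 visits and the primary analysis are complete.
- A reader might infer that most of the score is post-switch once the visit is 4 days early. That treats the visit day as wholly post-switch. With a pre-dose morning entry the share is 50%.
- A reader might put a figure on how many subjects are affected. The documents do not report visit timing, so any such figure would only restate an assumed spread of visits.

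**Conclusion.** The inconsistency is in the current text and affects the derivation of the primary endpoint. The windows coincide only for Visit 204 on Day 85. For an early visit, Table 2-1 as written scores the visit day and k-1 days wholly after the switch. A visit one day early therefore adds only the visit day, and wholly post-switch days begin with visits two days early. The dose changes only in the 72 mg arm. In the 120 mg arm the presentation and open-label status change.

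The possible effect per subject is bounded by 6 UAS7 points for each unshared day, the same size as the responder cut-off. The effect on the response rate cannot be derived, because neither the visit-date distribution nor the daily scores are given. The conclusion rests on two readings: that no numeric visit window applies, since the text gives none, and that the first PFS dose is given at the actual Visit 204.

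**What to change.** **Week 12 UAS7, HSS7 and ISS7.** State one rule in SAP 2.1.1.3.2 and 2.5.3 under which no diary day on or after the first PFS dose enters the score. For example: the 7 days ending on the day before the earlier of Day 85 and the actual Visit 204 or first PFS dose. This gives Days 78-84 when the visit is on time, late or missed, and the last 7 pre-switch days when it is early.

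**SAP section 4.** Record that the late-visit window departs from Protocol 12.4.1. For a visit on Day 92, for instance, the protocol's window is Days 85-91.

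**Cumulative AAS7 = 0 count.** Keep the non-overlapping study weeks, and drop days on or after the first PFS dose from Week 12 instead of shifting the window. Say that Week 12 AAS7 follows the existing missing-data rules when fewer than 4 days remain, which will be so for any visit 4 or more days early.

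**Cost.** A short SAP text change and one derivation change, with no new data. The pre-dose morning entry on the visit day is not used, and some Week 12 AAS7 values may become missing.
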